Appendix 1. Abbreviations44

PROTOCOL SUMMARY

In India, the 13-valent pneumococcal conjugate vaccine (13vPnC) is licensed for infants and children aged 6 weeks to 5 years and adults aged ≥ 50 years. Based on data from a recent Phase 4/3 study (B1851140) in children and adolescents aged 6 to 17 years in India, where 13vPnC elicited robust immune responses for all 13 serotypes, the Drug Controller General of India (DCGI) granted approval for this age group. To generate additional safety data in individuals aged 6 to 17 years in India, a Phase 4 safety study was requested by the DCGI. In this study, electronic diaries will be given to the parent(s)/legal guardian(s)/caregiver(s) to collect local reactions and systemic events for 7 days after vaccination. Investigators will collect other adverse events (AEs) at the follow-up visit 1 month after vaccination.

STUDY OBJECTIVES AND ENDPOINTS

Primary Objective(s):	Primary Endpoint(s):
To describe the safety profile of 13vPnC in pediatric subjects 6 to 17 years of age.	
Local reactions within 7 days after vaccination.Systemic events within 7 days after vaccination.AEs within 1 month after vaccination.

STUDY DESIGN

This is a Phase 4, open-label, single-arm, multicenter study in which subjects 6 to 17 years of age will receive 1 dose of 13vPnC.

Approximate Duration of Subject Participation

Subjects will participate in the study for approximately 1 month.

Approximate Duration of the Study

Based on an estimated enrollment period of 3 months, the total study duration will be approximately 4 months.

Number of Subjects

Approximately 100 subjects will be enrolled.

SCHEDULE OF ACTIVITIES

The schedule of activities table provides an overview of the protocol visits and procedures. Refer to the Study Procedures and Assessments sections of the protocol for detailed information on each procedure and assessment required for compliance with the protocol.

The investigator may schedule visits (unplanned visits) in addition to those listed on the schedule of activities table, in order to conduct evaluations or assessments required to protect the well-being of the subject.

Visit Number	1	2
Visit ID	Vaccination	Follow-up Visit
Visit Window (Days)	Day 1	28 to 42 Days After Visit 1
Informed consent (and assent if appropriate)	X	
Assign a subject identification number	X	
Demography	X	
Review inclusion criteria, exclusion criteria, and temporary delay criteria	X	
Medical history	X	
Physical examination	X	
Nonstudy vaccine data collection	X	X
Urine pregnancy test for female subjects of childbearing potential	X	
Confirm use of appropriate contraceptives throughout the study (if appropriate)	X	X
Prevaccination temperature	X	
13vPnC administration	X	
Assess acute reactions for at least 20 minutes after 13vPnC administration	X	
Provide 7-day e-diary, digital thermometer, and measuring device and provide instructions on their correct use	X	
Review e-diary data (Days 1 through 7; daily is optional)	X-----X	
Collect e-diary		X
AE and SAE collection	X-----X	

Abbreviations: e-diary = electronic diary

1. INTRODUCTION

1.1. Indication in India

The 13-valent pneumococcal conjugate vaccine (13vPnC) is being investigated for the following:

- Active immunization for the prevention of disease caused by *Streptococcus pneumoniae* serotypes 1, 3, 4, 5, 6A, 6B, 7F, 9V, 14, 18C, 19A, 19F, and 23F (including sepsis, meningitis, bacteremia, pneumonia, and acute otitis media) in infants and children from 2 months to 5 years of age.
- Active immunization for the prevention of pneumonia and invasive disease caused by *S pneumoniae* serotypes 1, 3, 4, 5, 6A, 6B, 7F, 9V, 14, 18C, 19A, 19F, and 23F in children 6 to 17 years of age.
- Active immunization for the prevention of pneumonia and invasive disease caused by *S pneumoniae* serotypes 1, 3, 4, 5, 6A, 6B, 7F, 9V, 14, 18C, 19A, 19F, and 23F in adults 50 years of age and older.

1.2. Background and Rationale

S pneumoniae infections are a significant cause of morbidity and mortality worldwide. In India, *S pneumoniae* is associated with high disease burden and mortality among young children.¹ Using modeling-based estimates, it is estimated that in 2010, about 3.6 million episodes of severe pneumonia and about 0.35 million all-cause pneumonia deaths occurred in children younger than 5 years of age in India.² Of these, it was estimated that about 0.56 million severe episodes of pneumococcal pneumonia and 105,000 pneumococcal deaths occurred in India. Older children are also affected, particularly those with certain underlying medical conditions, including diabetes mellitus, chronic cardiac or pulmonary disease, sickle cell disease, human immunodeficiency virus infection, other immunocompromising conditions, cochlear implants, or cerebrospinal fluid leaks.³

In India, 13vPnC is licensed for infants and children 6 weeks to 5 years of age and adults ≥ 50 years of age.⁴ Following a recent Phase 4/3 study (B1851140), which assessed the immunogenicity and safety of 13vPnC in 200 healthy children and adolescents aged 6 to 17 years in India, the Drug Controller General of India (DCGI) granted approval for this age group. In this study, 13vPnC elicited robust immune responses for all 13 serotypes, with statistically significant increases in opsonophagocytic activity (OPA) titers to all 13 serotypes. No adverse events (AEs) were reported by the caregivers at the follow-up visit 1 month after vaccination. In this study, electronic diaries (e-diaries) were not used by the caregivers to collect local reactions and systemic events that were anticipated after vaccination. Such reactions have been collected in other pediatric and adult studies,⁴ and from a US licensing study (6096A1-3011) in children and adolescents 15 months to 17 years of age.⁵ The US clinical trial included 294 children 5 to <10 years of age previously vaccinated with at least 1 dose of 7-valent pneumococcal conjugate vaccine (7vPnC), and 298 children and adolescents 10 to 17 years of age not previously vaccinated with 7vPnC.

In this study, 13vPnC was demonstrated to be immunogenic and an acceptable safety profile was demonstrated in subjects 6 to 17 years of age.

To generate additional safety data in children and adolescents aged 6 to 17 years in India, a Phase 4 safety study was requested by the DCGI. In this study, e-diaries will be given to the parent(s)/legal guardian(s)/caregiver(s) to collect local reactions and systemic events for 7 days after vaccination. Investigators will collect other AEs at the follow-up visit 1 month after vaccination.

Additional information for this compound may be found in the single reference safety document (SRSD), which for this study is the local package insert.

This study is defined as a postauthorization safety study (PASS).

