6.1. Visit 1 - Vaccination (Day 1)

- Obtain written informed consent and, if applicable, assent (age dependent on local requirement) before performing any study-specific procedures.
- Assign a subject identification number.
- Obtain and record the subject demography (including date of birth, sex, race, and ethnicity).
- Obtain and record any nonstudy vaccinations received from 28 days prior to vaccination.
- Obtain and record the medical history, including the presence of chronic conditions and/or medical history of significance.
- Perform physical examination evaluating any clinically significant abnormalities, including worsening of medical history conditions, within the following body systems: general appearance; skin; head, eyes, ears, nose, and throat; heart; lungs; abdomen; musculoskeletal; extremities; neurological; and lymph nodes.
- Collect and record any AEs and serious adverse events (SAEs) that occurred since the signing of the ICD.
- Perform a urine pregnancy test on female subjects of childbearing potential.
- Confirm use of appropriate contraceptives (if appropriate).
- On the day of vaccination, prior to vaccination, measure and record the subject's temperature using the preferred local method.
- Ensure that all of the inclusion criteria, none of the exclusion criteria, and none of the temporary delay criteria are met.
- Administer a single 0.5-mL injection of 13vPnC into the left thigh or the left deltoid muscle as appropriate for the subject.
- Observe the subject for at least 20 minutes after 13vPnC administration for any acute reactions. Record any AEs in the subject's source documents and on the AE section of the CRF.
- Issue an e-diary and provide instructions on its use for 7 days (Day 1 through Day 7, where Day 1 is the day of vaccination).
- Issue a measuring device and a digital thermometer and provide instructions on their use for 7 days (Day 1 through Day 7, where Day 1 is the day of vaccination).

- Ask the parent(s)/legal guardian(s)/caregiver(s) to contact the site staff or investigator immediately if the subject experiences redness or swelling at the injection site measuring greater than 7 cm (>14 measuring device units) from Day 1 to Day 7 after vaccination to determine if an unscheduled reactogenicity visit is required.
- Ask the parent(s)/legal guardian(s)/caregiver(s) to contact the investigator immediately if any significant illness or hospitalization occurs during the study period.

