6.2. Visit 2 - Follow-up Visit (28 to 42 Days After Visit 1)

- Review the subject's e-diary data and collect the e-diary. Collect stop dates of any e-diary events ongoing on the last day that the e-diary was completed and record stop dates in the CRF.
- Determine whether any AEs (including SAEs) have occurred since the last study visit and record them on the CRF (see [Section 8](#)).
- Collect and record any follow-up information on previously documented AEs and SAEs and record their end dates or confirm that they are still continuing.
- Record any nonstudy vaccinations.
- Confirm use of appropriate contraceptives (if appropriate).
- Complete the source documents and the CRFs.

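### Unsolicited AEs within 1 month, a primary endpoint, rest mainly on caregiver recall at Visit 2 and may be under-recorded; fixed neutral prompts at that visit would be a cheap improvement

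*Protocol*

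**What the plan says.** Protocol 1.2 describes study B1851140, "which assessed the immunogenicity and safety of 13vPnC in 200 healthy children and adolescents aged 6 to 17 years in India", and reports that "No adverse events (AEs) were reported by the caregivers at the follow-up visit 1 month after vaccination". It adds that in that study "electronic diaries (e-diaries) were not used by the caregivers to collect local reactions and systemic events that were anticipated after vaccination".

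For the present study the same section says that "e-diaries will be given to the parent(s)/legal guardian(s)/caregiver(s) to collect local reactions and systemic events for 7 days after vaccination", and then: "Investigators will collect other AEs at the follow-up visit 1 month after vaccination". Protocol 2 and SAP 3.1 list three primary endpoints: local reactions and systemic events, each within 7 days, and AEs within 1 month.

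Protocol 6.2 places Visit 2 at 28 to 42 days after Visit 1 and tells the investigator to "Determine whether any AEs (including SAEs) have occurred since the last study visit". Protocol 8.1.2 requires nonleading questioning and the recording of observed and spontaneously reported AEs. No other visit is scheduled after vaccination.

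There are further channels:
- a 20-minute observation after the injection (6.1);
- an instruction to families to "contact the investigator immediately if any significant illness or hospitalization occurs during the study period" (6.1), and to call about redness or swelling above 7 cm;
- staff review of e-diary data online during Days 1 to 7 (6.1, 7.3);
- a request to caregivers, attached to reactions that outlast the diary, to report these and any new AEs (7.3.1, 7.3.2).

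Protocol 9.1 (Table 4) gives the probability of observing at least one AE for a range of true event rates and sample sizes. SAP 5.2.1 and 6.3.1 plan Clopper-Pearson intervals for AE percentages.

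**The concern.** By the protocol's own account, caregiver report at a 1-month visit produced no AEs in a study where reactions were expected. That suggests events were missed. The e-diary is the protocol's response, and it is a good one for the events it lists during the week it covers. For everything else (ordinary illnesses, clinic visits, unlisted symptoms, anything after Day 7) the plan still relies mainly on what a caregiver remembers four to six weeks later.

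Under-recording would pull the third primary endpoint downwards. The planned exact intervals would not show this, because they reflect sampling error only. A result of 0/100, for instance, would be reported with an upper limit of 3.6% and could be read as reassurance when it partly reflects recall. The regulator asked for this study in order to obtain additional safety data, so that reading matters.

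**Working it through.** **The plan's own figure.** Table 4 uses P(at least one AE) = 1 − (1 − p)^n. With p = 1.0% and n = 100: 1 − 0.99^100 = 1 − 0.366 = 63.4%, as printed. The other cells also reproduce to the printed decimal. The formula puts the true event rate where the recorded rate belongs, so it assumes that every event is reported.

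**Inputs for the earlier study.** Numerator 0 and denominator 200, both from Protocol 1.2. Using 200 assumes that every child was assessed at the 1-month visit, which the protocol does not say.

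**Exact upper limit.** For 0/n the two-sided 95% Clopper-Pearson upper limit is 1 − 0.025^(1/n).
- n = 200: 1 − 0.025^(1/200) = 1.83%.
- n = 100 (a zero result in this study): 1 − 0.025^(1/100) = 3.6%.

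**How surprising is 0/200 if every event was captured?** P(0/200) = (1 − p)^200, where p is the true 1-month any-AE rate. The documents give no value for p, so these are assumed:

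| Assumed p | P(0/200) |
|---|---|
| 1% | 0.99^200 = 13% |
| 2.5% | 0.975^200 = 0.6% |
| 5% | 0.95^200 = 0.004% |

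A zero is unremarkable at 1% and hard to reconcile with full capture from about 2.5% upwards.

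**What each channel can pick up in this study.**

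| Channel | Actively elicits ordinary unsolicited AEs? |
|---|---|
| 20-minute observation | No: acute reactions only |
| E-diary and its online review | No: listed reactions, Days 1 to 7 |
| Call instruction | No: significant illness, hospitalization, large local reactions |
| Spontaneous reports; request to report new AEs | No: depend on the caregiver's initiative |
| Visit 2 enquiry | Yes, by recall over 28 to 42 days |

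Protocol 8.1.4 sets the collection period from consent through Visit 2, but it adds no contact within it.

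**The case against.** The strongest reply is that the earlier zero says little about this endpoint. The only events that Protocol 1.2 calls anticipated are local reactions and systemic events, and those are now recorded daily. For the remaining AEs the documents offer no rate that would make zero surprising; at 1% it has a 13% chance. The study is also descriptive, with no hypothesis test. All of this is true. It limits how strongly under-recording can be claimed, but it does not supply active elicitation where the plan has none.

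Several stronger readings are tempting but are not supported.
- A reader might infer that this study repeats the same procedure, a single interview with one general question. The documents do not describe how B1851140 elicited AEs, and they fix neither the number nor the wording of the Visit 2 questions. Other channels exist as well.
- A reader might infer that no AE of any kind occurred or was recorded in B1851140. The statement concerns caregiver report at the follow-up visit only.
- A reader might scale Table 4 down. Dividing 1.83% by an assumed any-AE rate of 10% gives at most 18% capture, and 1 − (1 − 0.01 × 0.18)^100 is about 16% in place of 63.4%. The same step gives about 31% if the assumed rate is 5% (37% capture) and about 60% if it is 2% (91% capture). The answer is set by the assumption. It also supposes that every type of AE is missed equally, although significant illness and hospitalization carry an instruction to call at once.

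**Conclusion.** The point holds as a cheap improvement to the plan. Unsolicited AEs within 1 month rest mainly on caregiver recall at 28 to 42 days, the rate may be underestimated, and Table 4 makes no allowance for this.

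The size cannot be fixed from the documents. What can be said is conditional: if all 200 children were assessed, the recorded rate in the earlier study has an exact 95% upper limit of 1.83%, and full capture becomes difficult to believe only if the true any-AE rate was about 2.5% or more.

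A reader might go further and call a very low rate likely in this study, or conclude that the trial adds little. Neither follows. Recording may differ from B1851140, and the two e-diary primary endpoints are unaffected and provide data that the earlier study did not collect by diary.

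**What to change.** In Protocol 6.2 and 8.1.2, specify fixed, vaccine-neutral prompts for Visit 2. Since vaccination, has the child:
- seen a health professional;
- taken any medicine;
- missed school or usual activity;
- had any new symptom?

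Each positive answer is followed up and recorded as an AE if it qualifies. The prompts suggest no particular vaccine reaction, so they are compatible with the nonleading rule in 8.1.2. The medicine question is only a memory aid and need not alter Protocol 5.5.2, under which permitted medication is not documented in the CRF.

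Optionally, add one daily yes/no e-diary item on any other illness or symptom. It should stay outside the completeness definition in SAP 3.5.1. Staff would follow up each positive answer and enter it on the AE page of the CRF if it qualifies, because Protocol 7.3 does not otherwise carry diary data into the CRF. This item is secondary: it covers Days 1 to 7 only and leaves the longer recall period to the Visit 2 prompts.

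The cost is a wording change and a short script, with no added visit. More minor background AEs will need follow-up and coding, and the diary item, if adopted, needs a small programming change.

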2. STUDY OBJECTIVES AND ENDPOINTS

Primary Objective(s):	Primary Endpoint(s):
To describe the safety profile of 13vPnC in pediatric subjects 6 to 17 years of age.	
Local reactions within 7 days after vaccination.Systemic events within 7 days after vaccination.AEs within 1 month after vaccination.

3. STUDY DESIGN

This is a Phase 4, open-label, single-arm, multicenter study in which subjects 6 to 17 years of age will receive 1 dose of 13vPnC.

3.1. Approximate Duration of Subject Participation

Subjects will participate in the study for approximately 1 month.

3.2. Approximate Duration of the Study

Based on an estimated enrollment period of 3 months, the total study duration will be approximately 4 months.

3.3. Number of Subjects

Approximately 100 subjects will be enrolled.

4. SUBJECT ELIGIBILITY CRITERIA

This study can fulfill its objectives only if appropriate subjects are enrolled. The following eligibility criteria are designed to select subjects for whom participation in the study is considered appropriate. All relevant medical and nonmedical conditions should be taken into consideration when deciding whether a particular subject is suitable for this protocol.

Subject eligibility should be reviewed and documented by an appropriate member of the investigator's study team before subjects are included in the study.

4.1. Inclusion Criteria

Subjects must meet all of the following inclusion criteria to be eligible for enrollment into the study:

1. Evidence of a personally signed and dated informed consent document (ICD) indicating that the subject's parent(s)/legal guardian(s) has/have been informed of all pertinent aspects of the study.

Note: The subject's assent may also be required depending on local requirements.

2. Healthy male or female children 6 to 17 years of age at the time of vaccination.
3. Parent(s)/legal guardian(s)/child willing and able to comply with scheduled visits, treatment plan, and other study procedures.
4. Male subject not able to father children, male subject who is able to father children and willing to use a highly effective method of contraception, female subject not of childbearing potential, or female subject of childbearing potential and at risk for pregnancy who is willing to use a highly effective method of contraception.

Note: Female subjects of childbearing potential are defined as female subjects ≥ 9 years old or have experienced menarche, whichever is earlier, and who are anatomically and functionally able to conceive.

4.2. Exclusion Criteria

Subjects with any of the following characteristics/conditions will not be included in the study:

1. Child who is a family member of:
 - Investigator site staff members directly involved in the conduct of the study;
 - Site staff members otherwise supervised by the investigator;
 - Pfizer employees directly involved in the conduct of the study.
2. Participation in other studies involving investigational drug(s) within 28 days prior to study entry and/or during study participation. Participation in observational studies is permitted.
3. History of severe adverse reaction, including hypersensitivity such as anaphylaxis, associated with a vaccine or vaccine component.
4. Contraindication to vaccination with pneumococcal conjugate vaccines (refer to local package insert).
5. Previous vaccination with licensed or investigational pneumococcal vaccine.

6. Bleeding diathesis or condition associated with prolonged bleeding time that would contraindicate intramuscular injection.
7. History of culture-proven invasive disease caused by *S pneumoniae*.
8. Major known congenital malformation or serious chronic disorder.
9. Known or suspected immune deficiency or suppression.
10. Other acute or chronic medical or psychiatric condition including recent (within the past year) or active suicidal ideation or behavior or laboratory abnormality that may increase the risk associated with study participation or investigational product administration or may interfere with the interpretation of study results and, in the judgment of the investigator, would make the subject inappropriate for entry into this study.
11. Pregnant females; breastfeeding females; fertile males and females of childbearing potential who are unwilling or unable to use a highly effective method of contraception as outlined in this protocol for the duration of the study.

4.3. Criteria for Temporarily Delaying Vaccine Administration

The following conditions are temporary or self-limiting and a subject may be vaccinated in the study once the condition has resolved and no other exclusion criteria are met.

1. Current febrile illness (temperature $\geq 100.4^{\circ}\text{F}$ [38.0°C]) or other acute illness within 48 hours before 13vPnC administration.

4.4. Lifestyle Requirements

4.4.1. Contraception

All fertile male subjects and female subjects who are of childbearing potential who are, in the opinion of the investigator, sexually active and at risk for pregnancy with their partner(s) must agree to use a highly effective method of contraception consistently and correctly for the duration of the study.

The investigator or his or her designee will confirm that the subject has selected an appropriate method of contraception from the list of permitted contraception methods (see below). At time points indicated in the Schedule of Activities, the investigator or designee will instruct the subject of the need to use highly effective contraception consistently and correctly and document the conversation, and the subject's affirmation, in the subject's chart. In addition, the investigator or designee will instruct the subject to call immediately if the selected contraception method is discontinued or if pregnancy is known or suspected in the subject or partner.

Highly effective methods of contraception are those that, alone or in combination, result in a failure rate of less than 1% per year when used consistently and correctly (ie, perfect use) and include the following:

1. Established use of hormonal methods of contraception associated with inhibition of ovulation (eg, oral, inserted, injected, implanted, transdermal), provided the subject plans to remain on the same treatment throughout the entire study and has been using that hormonal contraceptive for an adequate period of time to ensure effectiveness.
2. Correctly placed copper-containing intrauterine device (IUD).
3. Male condom or female condom used WITH a separate spermicide product (ie, foam, gel, film, cream, or suppository). For countries where spermicide is not available or condom plus spermicide is not accepted as highly effective contraception, this option is not appropriate.

NOTE: Sexual abstinence, defined as completely and persistently refraining from all heterosexual intercourse (including during the entire period of risk associated with the study treatments) may obviate the need for contraception ONLY if this is the preferred and usual lifestyle of the subject.

All sexually active male subjects must agree to prevent potential transfer to and exposure of partner(s) to drug through ejaculate by using a condom consistently and correctly, for the duration of the study.

